2. INTRODUCTION

PF-07328948 is a small molecule allosteric inhibitor/degrader of BDK that is currently being developed as an oral therapy to treat heart failure.

2.1. Study Rationale

This study will be the first time PF-07328948 is administered to humans. The purpose of the study is to evaluate the safety, tolerability, plasma PK and PD of PF-07328948 following administration of escalating, single, oral doses to healthy adult participants.

2.2. Background

Tissue and/or plasma BCAA and/or BCKA levels are elevated in various disease states including heart failure, type 2 diabetes mellitus, NAFLD/NASH, and obesity. 1,2,3,4 Furthermore, elevated BCAA levels in HF are associated with a loss of the BCAA catabolic machinery, 1,2 suggesting that the BCKDH pathway, involved in BCAA and BCKA catabolism, is dysregulated in cardiometabolic disease indications. Because inhibitory phosphorylation of BCKDH by BDK reduces BCAA catabolism, a BDK inhibitor would reduce BCKDH phosphorylation, thereby increasing BCAA and BCKA catabolism and reducing the elevated levels of BCAAs and BCKAs associated with several cardiovascular and metabolic diseases.

PF-07328948 is an orally administered, small molecule, potent allosteric BDK inhibitor that inhibits BCKDH phosphorylation in vitro and has consistently demonstrated robust, doseand time-dependent BCAA and BCKA lowering in plasma and tissues in mouse, rat and/or

These improvements were concomitant with reduced pBCKDH and BDK levels in heart and kidney tissue as well as reduced plasma BCAA and BCKA levels.

2.2.1. Nonclinical Pharmacology

PF-07328948 is a potent antagonist of mouse, rat, dog, and human BDK In human skeletal muscle cells, PF-07328948 treatment resulted in inhibition of BDK-dependent phosphorylation of BCKDHA. In HEK293 cells, PF-07328948 decreased both BDK protein and the ratio of pBCKDHA/BCKDHA protein.

diet-induced obese mice, reductions of plasma BCAAs and BCKAs were observed following subchronic and chronic dosing. PF-07328948 reduced liver triglycerides, plasma insulin levels, and plasma non-esterified free fatty acids after chronic dosing compared with vehicle-

liver, and portal inlet. CCI

treated animals. These metabolic improvements were concomitant with decreases in BDK protein levels in gastrocnemius muscle and heart, and decreased phosphorylation of BCKDH in muscle, heart, and liver. In the ZSF1 rat model of heart failure-preserved ejection, after chronic administration in food, PF-07328948 improved exercise capacity and increased systolic cardiac functional parameters, with a trend for reduced left atria hypertrophy compared to animals that were administered control chow. These improvements were concomitant with reduced pBCKDH and BDK levels in heart and kidney tissue as well as reduced plasma BCAA and BCKA levels.

Details of the nonclinical pharmacology are included in the IB.

2.2.2. Nonclinical Pharmacokinetics and Metabolism

PF-07328948 was rapidly absorbed with moderate to high oral bioavailability and had low to moderate plasma CL and V_{ss} in rats, dogs, and monkeys. After IV administration of PF-07328948, renal excretion of unchanged PF-07328948 was <1% in rats, dogs, and monkeys and biliary excretion of unchanged PF-07328948 was ~1% in rats. In oral repeat-dose toxicity studies in rats and dogs, the systemic exposure increased with increasing dose in a less than or approximately dose proportional manner and there were no consistent sex-related differences or accumulation observed.

PF-07328948 was highly bound to plasma proteins in all species evaluated, with binding that was concentration dependent and was preferentially distributed into plasma relative to blood CCI

[figure not shown]
The DDI potential was further evaluated with a static mechanistic model using the projected C_{max} for reversible inhibition or C_{ave} for induction in plasma, intestinal lumen, enterocytes,

These predictions will be refined once human PK data are available for PF-07328948.

Additional details are included in the IB.

2.2.4. Nonclinical Safety

Based on a weight of evidence, PF-07328948 does not pose a risk for genotoxicity.

Based on the UV absorption profile of PF-07328948, there is a potential for phototoxicity.

Additional details of the nonclinical safety are provided in the IB.

2.3. Benefit/Risk Assessment

Study C4921001 is the first time that PF-07328948 will be administered to humans and is designed primarily to generate safety, tolerability, and PK and PD data for further clinical development. PF-07328948 is not expected to provide any clinical benefit to healthy participants. The purpose of this study is to provide the basis for further clinical development of PF-07328948 as a first-in-class therapy for treatment of patients with heart failure. As of the date of final protocol, no specific human risks have been identified; postulated risks based on nonclinical studies are summarized in Section 2.3.1. The clinical impact of these potential risks will be minimized through the proposed cautious dose-escalation process wherein higher doses of PF-07328948 will be administered only after lower doses have been found to be well tolerated with an acceptable safety profile. Use of stopping rules for dose-escalation, as well as by specific safety monitoring measures, have been incorporated into this study, where appropriate, as outlined in the SoA. In addition, this study will use precautionary sentinel dosing in periods evaluating escalating doses of PF-07328948, and all periods will include standard, intensive, inpatient monitoring of the participants following administration of single, oral doses of the study intervention.

More detailed information about the known and expected benefits and risks and reasonably expected AEs of PF-07328948 may be found in the IB, which is the SRSD for this study.

2.3.1. Risk Assessment

All study intervention risks are communicated through the IB.

Potential Risk of Clinical Significance	Summary of Data/Rationale for Risk	Mitigation Strategy
	Study Intervention - PF-07328948	,
Effects on blood pressure	Decreased BP was observed after single doses (≥ 20 mg/kg) of PF-07328948 in dogs in exploratory toxicology studies. No BP changes were subsequently noted in GLP toxicology studies after single doses of ≤ 100 mg/kg in dogs.	 Participants will be in a closely monitored environment while in the CRU during the study. Inpatient monitoring will include serial assessment of blood pressure.
Skin sensitivity to light; sunburn	Based on light absorption within the UV range, PF-07328948 has a risk for phototoxicity.	 Participants with a history of phototoxicity or photosensitivity are excluded from study. Lifestyle and activity considerations have been added advising participant to use sunscreen and eye protection, and to avoid sunlight and high-intensity UV light exposure.
Drug-drug interactions resulting in exposure changes of background concomitant medications.	CCI	Use of prescription or nonprescription drugs and dietary and herbal supplements are prohibited within 7 days or 5 half-lives (whichever is longer) prior to the first dose of study intervention through the last PK collection.
Idiosyncratic drug reaction	IADR risk CCI	 Participants will be in a closely monitored environment while in the CRU during the study. Risk of IADR after single dose of PF-07328948 is considered low.
		Laboratory safety tests include serial assessment of LFTs and CBCs.

Potential Risk of Clinical Significance	Summary of Data/Rationale for Risk	Mitigation Strategy
BCAA deficiency	BCAAs play a multifaceted role in maintenance of health. Prolonged deficiency of ≥ 1 BCAA caused by excessive dietary restrictions in children associated with neurodevelopmental delays-function mutations in BDK gene in humans are associated with neurological sequelae.	 Single doses of PF-07328948 are not anticipated to result in prolonged lowering of BCAAs. Risk of neurological sequelae from magnitude and duration of BCAA lowering expected following single doses of PF-07328948 is considered very low. Neurological examination as part of the physical exam will be performed pre- and post-dose.
	Other	
The COVID-19 pandemic may pose risks to study participation.	During the pandemic, healthy participants could be infected with the SARS-CoV-2 virus through study participation, which could lead to increased health risks for this participant and others in the study. AEs could be confounded.	Inclusion of COVID-19 specific assessments according to the SoA.

2.3.2. Benefit Assessment

The participants in this study are not expected to obtain any specific benefit beyond contributing to the process of developing new therapies in an area of unmet need. They will receive close monitoring of their safety via study procedures undertaken (eg, physical examinations, including neurological examinations, 12-lead ECGs, vital signs) which will occur as outlined in this protocol.

2.3.3. Overall Benefit/Risk Conclusion

Based on the totality of available nonclinical data, and taking into account the measures to minimize risk to study participants, the overall benefit/risk profile supports clinical testing of PF-07328948 in this study as part of the clinical development for an indication of heart failure.

3. OBJECTIVES AND ENDPOINTS

Objectives	Endpoints
Primary:	Primary:
To evaluate the safety and tolerability of single ascending doses of PF-07328948 administered orally to healthy adult participants.	Assessment of adverse events, clinical safety laboratory tests, vital signs, continuous cardiac monitoring, 12-lead electrocardiograms, and physical examinations.
Secondary:	Secondary:
To evaluate the pharmacokinetics of PF-07328948 following single doses of PF-07328948 administered orally to healthy adult participants.	PK parameters derived from plasma PF-07328948 concentrations: C _{max} , T _{max} , AUC _{last} , and if data permit, AUC _{inf} , and t _½ .
Tertiary/Exploratory:	Tertiary/Exploratory:
To evaluate additional pharmacokinetic parameters of PF-07328948 following single doses of PF-07328948 administered orally to healthy adult participants.	Additional PK parameters derived from plasma PF-07328948 concentrations: C _{max} (dn), AUC _{last} (dn) and if data permit AUC _{inf} (dn), CL/F and V _z /F.
• CCI	
To evaluate the effect of food (eg, a protein-rich meal such as MMTT), if administered, on the plasma PK of PF-07328948 following single dose of PF-07328948 administered orally to healthy adult participants.	PK parameters derived from plasma PF-07328948 concentrations after MMTT: C _{max} , T _{max} , AUC _{last} , and if data permit, AUC _{inf} , and t _½ .

4. STUDY DESIGN

4.1. Overall Design

This is a randomized, investigator- and participant-blind, sponsor-open, placebo-controlled, first-in-human, single ascending oral dose, 4-period, sequential, crossover study of PF-07328948 administered to healthy adult participants. Approximately 24 healthy adult participants (up to 3 cohorts of approximately 8 participants each) will be enrolled in this study. The first 2 cohorts are planned, and the third cohort is optional. In each period, participants will be randomized to either PF-07328948 or placebo in a ratio of 3:1. Each participant is planned to undergo up to 4 treatment periods receiving up to 4 doses of PF-07328948 and up to 2 placebo.

Precautionary sentinel dosing will be used in any period evaluating escalating doses of PF-07328948 and may be omitted for periods when repeating a dose level or administering a lower dose level than previously evaluated. For periods with sentinel dosing, 2 participants (1 receiving PF-07328948 and 1 receiving placebo) will be dosed initially before the remaining participants of that period are dosed. Safety and tolerability data through at least 24 hours post-dose for the sentinel participants will be reviewed prior to dosing the remaining participants of that period.

Participants confirming eligibility according to Section 5 will be admitted to the CRU on Day -2 in Period 1 for each cohort and the 1st food period (if applicable) within a cohort. For all other periods (ie, Periods 2-4 except the 1st food period within each cohort), participants will be re-admitted to the CRU on Day -1. For each period in this study, on Day 1, following ≥10-hour overnight fast, participants will receive a single oral dose of PF-07328948 or placebo. Participants have been discharged on Day 3 in Cohort 1 and will be discharged on Day 4, following completion of all scheduled assessments out to 72 hours post-dose in Cohort 2 and optional Cohort 3. Participants may stay in the CRU after completion of Day 4 activities at the discretion of the investigator. In each cohort, a washout interval of at least 7 days will be introduced between subsequent doses. During the washout interval, emerging 24-hour PK and 48-hour safety data will be reviewed and the next dose will be determined. An on-site follow-up visit on Day 8±1 after the final dose and a final follow-up within 28-35 days after the final dose will be scheduled. Final follow-up may be a phone contact or an on-site visit at the discretion of the PI.

Based on the review of emerging safety, tolerability, and PK data (and PD data if available) in Cohorts 1 and 2, the optional third cohort may enroll 8 participants (crossover, placebo-controlled design) to explore additional doses, to repeat a dose, to evaluate split dosing, or to investigate food effects on PK and PD biomarkers.

Dosing will occur in the fasted state for all periods for dose escalation. The effect of a high-protein meal on safety, tolerability, PK exposure, and PD biomarkers may be assessed in at least 1 period within Cohort 2 and/or Cohort 3.

Participants should only need to undergo these time-matched assessments of PD biomarkers on Day -1 once in the fasted state and/or once in the fed state in each cohort, unless there is any uncertainty regarding the reliability of the initial Day -1 assessment. In addition, if thought necessary to achieve study objectives, study intervention may be administered in the fed state (eg, following a high-protein meal) during any of the study periods/cohorts.

The total duration of participation from the screening visit to the telephone follow-up contact will be approximately 14 weeks.

If a participant drops out before completing all study periods within a cohort, or withdraws for a reason unrelated to safety, the participant may be replaced at the discretion of the investigator and sponsor. The replacement participant(s) may or may not be required to complete all periods of the cohort in which they are participating at the discretion of the investigator and sponsor. Of note, replacement participants may be required to undergo time-matched assessments of PD biomarkers during Day -1 of their initial period in the study.

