This is a randomized, investigator- and participant-blind, sponsor-open, placebo-controlled, first-in-human study to assess safety, tolerability, PK and PD of single ascending oral doses of PF-07328948 administered to healthy adult participants in 2 planned cohorts (Cohort 1 and Cohort 2). Each cohort will be a 4-period, sequential, crossover, placebo-controlled design, with a washout interval of at least 7 days between doses. Precautionary sentinel dosing will be used in any period evaluating escalating doses of PF-07328948. Sentinel dosing may be omitted for periods when repeating a dose level or administering a lower dose level than previously evaluated. Safety and tolerability data through at least 24 hours post-dose for the sentinel participants will be reviewed prior to dosing the remaining participants

of that period. Participants will be screened for the eligibility criteria as listed in Section 5, within 28 days prior to administration of the first dose for each cohort.

Based on the review of emerging safety, tolerability, and PK, 1 optional cohort of 8 participants may be enrolled (crossover, placebo-controlled design) to explore additional doses, to repeat a dose, to evaluate split dosing, or to investigate food effects on PK and PD biomarkers.

Number of Participants: A total of up to approximately 16 (Cohorts 1 and 2) or 24 (with optional Cohort 3) healthy adult participants (approximately 8 participants per cohort) will be enrolled in the study.

Note: "Enrolled" means a participant's agreement to participate in a clinical study following completion of the informed consent process and randomization to study intervention. A participant will be considered enrolled if the informed consent is not withdrawn prior to participating in any study activity after screening. Potential participants who are screened for the purpose of determining eligibility for the study, but do not participate in the study, are not considered enrolled, unless otherwise specified by the protocol.

Study Population: Key inclusion and exclusion criteria are listed below:

Inclusion Criteria

Participants must meet the following key inclusion criteria to be eligible for enrollment into the study:

- 1. Female participants of non-childbearing potential and males must be 18 to 60 years of age, inclusive, at the time of signing the ICD.

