1.2. Schema

Figure 1. Study Design Schema^{a,b,c,d}

- a. Doses shown for each cohort except the starting dose in Cohort 1 are planned doses and may be modified based on emerging data from previous cohorts. Similarly, assignment to study intervention may be modified. n represents number of participants
- b. Effect of food (eg, a protein-rich meal such as MMTT) may be evaluated in at least 1 period of Cohort 2 (eg, P3) and/or Cohort 3
- c. In the first period in each cohort (with red box) and the first period of assessment of food effect in any cohort (eg, P3 in Cohort 2 with red box), participants will be admitted on Day -2 and time-matched biomarker assessment will be collected on Day -1.
- d. Precautionary sentinel dosing will be used in any period evaluating escalating doses of PF-07328948. For such periods, 2 participants (1 receiving PF-07328948 and 1 receiving placebo) will be dosed initially before the remaining participants of that period are dosed. Safety and tolerability data through at least 24 hours post-dose for the sentinel participants will be reviewed prior to dosing the remaining participants of that period. Sentinel dosing may be omitted when repeating a dose level or administering a lower dose level than previously evaluated.

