4.2. Scientific Rationale for Study Design

The population planned for this study will be healthy males and females of non-childbearing potential. Female participants will be confirmed not to be of childbearing potential because embryo-fetal development toxicity studies with PF-07328948 have not been conducted. In male participants, appropriate measures are expected to be followed to minimize potential transfer of PF-07328948 via semen to partners (see Appendix 4).

Because this is the first time PF-07328948 will be administered to humans, an escalating single, oral dose, crossover design is planned with careful assessment and ongoing review of safety, tolerability, and PK data of PF-07328948. Precautionary sentinel dosing will also be utilized in any period evaluating escalating doses of PF-07328948 to ensure that safety and tolerability data in a subset of 2 participants within each period supports testing additional participants in that period. In each period, approximately 6 participants are planned to receive PF-07328948, and approximately 2 participants are planned to receive placebo, with all the participants at the end of the study having received up to 4 doses of PF-07328948 and up to 2 placebo. The crossover design permits both within- and between-participants assessments of safety, tolerability, and PK at multiple dose levels and placebo.

In addition, the highest anticipated C_{max} and AUC_{24} of PF-07328948 will not exceed the pre-defined human exposure stopping limits nor exceed the highest feasible total daily dose Eurthermore, to permit an unbiased assessment of safety, the administration of both PF-07328948 and placebo in each period will be double-blinded to both site staff (except those involved in preparation of doses) as well as participants. To permit real-time review of the safety, tolerability, and PK data, a limited number of sponsor study team members will be unblinded.

CCI

. As a BDK inhibitor/degrader,

PF-07328948 is expected to inhibit BDK-mediated phosphorylation of BCKDH enzyme complex, resulting in an increase in BCAA/BCKA catabolism and a decrease in circulating BCAA and BCKA levels. As protein intake is known to impact plasma BCAA/BCKA levels, CCI

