The PF-07328948 starting dose level of 10 mg is planned. The predicted PF-07328948 C_{max,u} and AUC_{24,u} after single dose of 10 mg are below the exposure limits defined for PF-07328948 dose escalation in Section 4.3.3. The maximum reduction for plasma isoleucine and ketoisoleucine are predicted to be 3% and 4%, respectively, suggesting little target modulation at this dose. A single dose of 1500 mg (the top dose in Table 3) is estimated to provide an exposure margin respectively, relative to the exposure limits.

The dose range to be studied was selected to account for uncertainties in the projected $C_{\rm eff}$ and the projected therapeutic dose, while also bracketing the expected clinically effective dose range in humans for clinically relevant pharmacological activity and providing safety coverage for a wide range of PF-07328948 doses.

Assessment of the safety, tolerability, and PK after each single dose level will be conducted before escalating to the next dose level. The dose/exposure-escalation increments are planned to be up to approximately semi-logarithmic increases in exposure from the previous highest dose level that has been evaluated. If exposure exceeds the projected therapeutic range, or if changes in safety parameters are observed, smaller dose-escalation steps may be implemented.

The actual dose levels, target exposures, and/or dose level increments may be adjusted (higher or lower) during the study based on emerging human safety, tolerability, and PK data, but projected exposures will not exceed the predefined human exposure limits. If C_{max} -related adverse events are observed, split dosing (eg, the total dose will be divided into 2 or 3 parts on Day 1) may be used to potentially increase AUC without increasing C_{max} . Dose levels may also be repeated if warranted.

When the assessment of the effect of food on the PK and PD of PF-07328948 is conducted, the dose level will be selected based on emerging safety, tolerability, and PK data from previous periods of this study. The actual dose level used will be expected to achieve exposures similar to or greater than projected therapeutic exposures (as outlined in Section 4.3.2).

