6.6.1. Dose Escalation and Stopping Rules

Precautionary sentinel dosing will be used in periods where escalating doses of PF-07328948 will be evaluated and may be omitted when repeating a dose level or administering a lower dose level than previously evaluated. Two participants (1 receiving PF-07328948 and 1 receiving placebo) within a period will be dosed initially before the remaining participants of that period are dosed. Safety and tolerability data through at least 24 hours post-dose for the sentinel participants will be reviewed prior to dosing the remaining participants of that period.

Dose escalation stopping rules will be used to determine whether the maximal tolerated dose has been attained. Dose escalation may be stopped if it is determined that the limits of safety and/or tolerability have been reached. This decision will be made after a discussion takes place between the sponsor study team and the investigator. The sponsor study team may not overrule the investigator's decision to stop dose escalation. If dose escalation is stopped because of any of these criteria, additional cohorts may receive the same or lower doses of the study intervention.

The dose escalation will be terminated based on the following criteria:

- If 50% or more of the participants receiving active drug at a given dose level (but not participants receiving placebo) develop similar clinically significant laboratory, ECG, or vital sign abnormalities, in the same organ class, indicating dose-limiting intolerance.
- Severe nonserious AEs, considered as, at least, possibly related to study intervention administration, in 2 participants at a given dose level (but not participants receiving placebo), independent of within or not within the same system organ class, indicating dose-limiting intolerance.
- Dosing will be paused for any SAE that occurs in a participant receiving active treatment until causality is fully assessed by the PI and sponsor. Dosing may resume if the SAE is determined to be not drug-related by the PI and sponsor. If the SAE is determined to be either drug-related or unknown, either dosing will cease or the SAE will be evaluated by the sponsor's protocol review committee (or similar review group), which is independent of the study team and investigators. If the protocol review committee determines that dosing may resume, a plan that mitigates risks to participants with the resumption of dosing will be implemented. Such a plan could

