#### 5.2. General Methods

Unless otherwise stated, all summaries and plots will be presented by treatment. If a dose level is repeated across 2 or more cohorts, the data will be combined, unless the dose is in a different food state (e.g. after an MMTT), in which case the dose would be reported separately.

Unless otherwise stated the summary tables and/or statistical analyses will only include a single pooled placebo group across all included cohorts. Placebo will be pooled from all dose escalation periods but not the fed period.

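### The sentinel exemption depends on dose level and ignores food state, so a fed period at a dose tested only fasted may be run without sentinels

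*Protocol*

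**What the plan says.** The protocol states the exemption four times, always in terms of dose level:

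- Section 1.1: "Sentinel dosing may be omitted for periods when repeating a dose level or administering a lower dose level than previously evaluated".
- Section 1.2, schema note d: "Sentinel dosing may be omitted when repeating a dose level or administering a lower dose level than previously evaluated".
- Section 4.1: "may be omitted for periods when repeating a dose level or administering a lower dose level than previously evaluated".
- Section 6.6.1, the operative rule: "may be omitted when repeating a dose level or administering a lower dose level than previously evaluated".

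SAP Section 2.3 repeats it in the text and in Figure 1 note d. Two further protocol sections give only the requirement. Section 4.2 says "Precautionary sentinel dosing will also be utilized in any period evaluating escalating doses of PF-07328948", and Section 2.3 says "this study will use precautionary sentinel dosing in periods evaluating escalating doses of PF-07328948".

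On food, Protocol Section 4.1 keeps escalation periods fasted. It allows a high-protein meal to be assessed in Cohort 2 and/or Cohort 3, and more generally allows fed dosing in any period or cohort. Section 4.3.4 says that the fed dose will be chosen from earlier data in the study and should give exposure at or above the projected therapeutic range. The first food period in a cohort has its own admission and biomarker rule (Day -2 and Day -1). None of the food provisions (Protocol 4.1, 4.3.4, 5.3.2, 6.1.1) contains a sentinel rule.

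Elsewhere the plan does treat food state as a separate condition. SAP Section 5.2 pools a repeated dose level across cohorts "unless the dose is in a different food state (e.g. after an MMTT), in which case the dose would be reported separately".

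**The concern.** Sentinels protect the group when participants are dosed under conditions not yet tried in humans. Appendix 9 of the protocol records that they were added against unpredicted risks. Escalation is governed by exposure: the increments in Section 4.3.4 and the limits in Section 6.6.1 are exposure quantities. A meal can change exposure at a fixed dose, so a dose level given only fasted does not settle what the same dose does when fed.

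As worded, the first fed period at such a dose is a repeat or a reduction and qualifies for the exemption. If food raises exposure and the fed dose is near the top of the tested range, the group could reach exposures above any mean yet seen. About 6 participants on active drug would then be dosed without the 24-hour sentinel review.

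**Working it through.** **Text check.** (1) Sentinels are required only for escalating doses. (2) Escalation periods are fasted. (3) A fed period at a dose already given fasted is therefore not an escalation, but a repeated or lower dose level. (4) The exemption covers repeated and lower dose levels and has no food condition. (5) No food provision adds a requirement. Sentinels may therefore be omitted.

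**Size.** The plan gives no figure for this point, so the arithmetic is illustrative. Inputs are the Table 3 predictions (total Cmax in ng/mL, total AUC24 in ng·h/mL, unbound values in brackets) and the Section 6.6.1 limits: unbound Cmax 285 ng/mL, unbound AUC24 3250 ng·h/mL.

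| Dose | Cmax | AUC24 |
|---|---|---|
| 300 mg | 13800 (20) | 81500 (112) |
| 750 mg | 34600 (64) | 181000 (286) |
| 1500 mg | 69200 (173) | 310000 (595) |

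*Rise at 1500 mg that reaches the Cmax limit.* With a constant unbound fraction: 285/173 = 1.65-fold. Table 3, however, assumes that the unbound fraction rises with concentration. Its linear equation is redacted, so I fitted a line to the three fractions 20/13800, 64/34600 and 173/69200. The fit is 0.00119 + 1.895e-8 × C, where C is total Cmax, and it returns 20.0, 63.9 and 173.1. For a rise r in total Cmax at 1500 mg:

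unbound Cmax = 69200r × (0.00119 + 1.895e-8 × 69200r) = 82.35r + 90.74r².

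Setting this to 285 gives r = 1.38 (1.37 to 1.39 if the rounded unbound values are varied by 0.5). The range is therefore about 1.4- to 1.65-fold.

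*What the existing cap would do at 1500 mg.* A projected 2-fold rise gives 346 (constant fraction) to 528 ng/mL (fit) and is already barred. A 1.25-fold rise gives 216 to 245 ng/mL, which the cap allows although it is above the 173 ng/mL predicted fasted.

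*Rise needed just to pass the 1500 mg fasted mean*, if fasted dosing has reached 1500 mg. The first figure is the total ratio and the second is the unbound ratio at constant fraction:

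| Fed dose | Cmax | AUC24 |
|---|---|---|
| 1500 mg | any rise | any rise |
| 750 mg | 69200/34600 = 2.00; 173/64 = 2.70 | 310000/181000 = 1.71; 595/286 = 2.08 |
| 300 mg | 69200/13800 = 5.01; 173/20 = 8.65 | 310000/81500 = 3.80; 595/112 = 5.31 |

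AUC24 is not the binding limit: 3250/595 = 5.46-fold headroom at 1500 mg.

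**What a sentinel adds.** Assume an event rate p of 10% to 30% on active drug, visible within 24 hours. One active sentinel shows an event with probability p, that is 0.10 to 0.30. Among 6 active participants the probability of at least one event is 1 − (1 − p)^6 = 0.47 to 0.88. If a sentinel event stops the period, expected events fall from 6p to p + (1 − p) × 5p: from 0.60 to 0.55 at 10%, and from 1.80 to 1.35 at 30%.

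**The case against.** The strongest reply is that the exemption only permits omission. Harm needs several things together: the sponsor omits sentinels, the fed dose is near the highest tested, food raises exposure, and the rise is not foreseen. The schema's planned doses and the projected efficacious dose are not visible, nor is any food-effect size or direction, so a 1500 mg fed period is an assumption. So is a 1500 mg fasted ceiling, since Section 6.1 allows doses up to 3000 mg. Table 3 holds predictions that observed PK may replace. All of this stands, and it limits the weight of the point.

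Safeguards also apply to fed periods. Section 4.3.4 says that "projected exposures will not exceed the predefined human exposure limits". Safety data to 48 hours and PK to 24 hours are reviewed before the next dose, a serious event on active drug pauses dosing, and participants are monitored as inpatients. These reduce the risk. But before the first fed period the projection contains no fed data from the study, and the observed-exposure limit acts only after the group has been dosed. Projections can also miss: Section 4.2 reports a half-life in Cohort 1 that may be longer than the predicted 4 hours.

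It is also fair to say that the remedy is modest. Sentinel review covers safety and tolerability at 24 hours. It does not measure fed PK, and one active participant detects little. And SAP Section 5.2 is a reporting rule, not evidence about dosing safety. It shows only that the plan already separates dose level from food state.

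**Conclusion.** The gap in the wording is real: a fed period at a dose tested only fasted may be run without sentinels, in the first case before any human fed data exist. It is a low-to-moderate safety gap. It matters mainly at or near the highest fasted dose with an upward food effect, and it is small when the fed dose is well below that. The figures rest on Table 3 predictions, on a fitted stand-in for the redacted binding equation, and on 1500 mg as the highest fasted dose.

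A reader might infer three stronger things that the documents do not support:

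- That the fed period will be run without sentinels. The text permits this and does not direct it.
- That participants could knowingly be dosed above the exposure limits. Projected exposure above them is barred.
- That 285 ng/mL marks toxicity. It is a limit that stops escalation, set from the no-adverse-effect exposure in the rat study.

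**What to change.** Make two insertions in Protocol Sections 1.1, 1.2 (note d), 4.1 and 6.6.1, and in both SAP Section 2.3 copies (text and Figure 1 note d).

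1. After the requirement for escalating doses, add: *and in any fed period whose dose is higher than any dose previously evaluated in the fed state in this study (including the first fed period of the study)*.
2. At the end of the exemption, add: *in the same food state*.

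Both are needed. Narrowing the exemption alone would leave the first fed period neither required nor exempt, because the present requirement covers only escalating doses. Defining the trigger by the highest dose already given fed in the study also covers a later, higher fed dose, and it avoids doubt over whether first means per study or per cohort. Add insertion 1 in Protocol Sections 2.3 and 4.2 so that the requirement reads the same throughout.

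The cost is wording in six protocol places and two SAP places, and about one day's delay for the remaining participants in each such period. That delay also applies at low fed doses, where the concern is small. Sample size, randomization and assessments do not change.
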